Study design: This is a randomized, double-blind, sham-controlled, clinical trial. The primary intervention is 30 minute sessions, 3x/week, for 12-13 weeks of transcutaneous tibial nerve stimulation sessions carried out at home. The sham intervention will consist of the same treatment schedule, except with the application of transcutaneous nerve stimulation to the lateral aspect of the lower leg, away from the tibial nerve. Patients will undergo a 12-13 week treatment course. The patient and the treating physician will be blinded to the group assignment of the patient. Randomization will be done using a random number generator, and study assignment will only be released at the end of the study. Only the study nurse instructing the patient on placement of the study electrodes will know the patient assignment. The effectiveness of our sham protocol will be evaluated with a question during week 2-3 asking if they think they are in the active or sham group. The study visit schedule is outlined in figure 1.

Figure 1. Proposed study schedule

STUDY SCHEDULE	Visit 1 Screening	Visit 2 Randomization	Telephone Followup	Visit 3 End of study
Visit Windows	1- 4 weeks prior to Randomization	Week 0	Every 2-3 Weeks	12-13 Weeks
Documentation of Consent	X			
Medical History and Physical Exam	X			
Inclusion/ Exclusion Criteria Review	X			
Medication and Health Review	X			X
Urine Pregnancy Test	X			
PPBC Questionnaire	X		X (week 6-7 only)	X
Qualiveen-SF/NBSS Questionnaire	X			X
3 day Voiding diary	Diary Provided	Completed Diary Returned & Provided for Visit 3		Completed diary returned
24hr Urinary Pad test	Supplies Provided with instruction	Pads Returned & Provided for Visit 3	Pad test done 1-7 days prior to visit 3	Pads Returned
Randomization		X		
Initial 30 minute treatment session in clinic with nurse supervision		X		
Assessment of treatment masking			X (week 2-3 only)	
Assessment of compliance, review instructions, address any adverse events or questions			X	
Physician assessment of benefit				X

Inclusion criteria

1. >18 years of age, with a clinical condition associated with neurogenic bladder dysfunction (multiple sclerosis, Parkinson's disease, stroke, dementia, cerebral palsy, spinal cord injury)(27).
2. Failure of behavioral measures and/or pharmacologic therapy to adequately control neurogenic bladder symptoms.

Exclusion criteria

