rehabilitation(28,29). Two adhesive patch electrodes will be applied to one of the patient's lower limb, and the location used will be based on their treatment assignment (active treatment versus sham). The initial treatment will be carried out in the clinic under the supervision of the investigating physician, with training provided for the patient on proper use of the device by the study nurse. The remaining treatments will be detailed on a calendar for the patient, with telephone contact every 2-3 weeks with research staff to assess compliance. When undergoing active treatment, patients will have the electrodes applied posterior to the medial malleolus, and 5-10 cm above the medial malleolus of the same leg, just behind the medial tibial edge. As per previous studies involving transcutaneous posterior tibial nerve stimulation for neurogenic bladder and overactive bladder(30-33) and similar to percutaneous tibial nerve stimulation(26), we will use the bipolar stimulation setting, with a frequency of 10 Hz, 200ms pulse, and the amplitude will be titrated up to patient's maximum non-painful tolerance or toe twitch in the case of complete SCI(30) (between 0.5-20mA). For patients undergoing sham treatment, they will have the patch electrodes placed on the lateral side of the lower limb, and instructed to keep the current setting stable at 1mA. This will prevent any meaningful stimulation of the tibial nerve, while still delivering a slight tingling sensation to simulate active treatment.

Primary outcome measure: We will use Patient Perception of Bladder Condition question, which is a common used endpoint in overactive bladder studies. Although it has not been formally studied in neurogenic bladder, its face validity is high, and it has been used for this purpose in the past(34). It is an ordinal scale from 0-5 ("My bladder does not cause me any problems at all" to "my bladder causes me many severe problems"). In the general population it is a valid, reliable and responsive single question(35). Patients will be categorized as responders (score improvement by 2 points between screening visit 1 and end of study visit 3) or non-responders.

Secondary outcome measures:

1. Neurogenic bladder symptom score (NBSS): valid and reliable tool for assessing neurogenic bladder symptoms(36).
2. The Qualiveen-SF is a measure of neurogenic bladder related QOL, which has been specifically shown to valid, reliable and responsive in neurogenic bladder(37,38).

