3. 3-day voiding diary parameters (daily voiding frequency, functional bladder capacity, mean voided volume, longest time between voids, nocturia, number of urgency incontinence episodes). This is a valid and reliable measure of urinary symptoms(39).
4. Quantification of urinary incontinence with 24hr pad weights. This is stable, reliable and responsive measure of the degree of urinary incontinence(40,41), and will be analyzed for the subgroup of patients with incontinence.
5. Physician assessment of benefit will be completed based on a standard clinical history at study visit 3 (end of study), and graded on a 7 point global response assessment.

Sample size: Using previous percutaneous tibial nerve stimulation studies as a guide(26), we estimate 20% of sham patients and 60% of actively treated patients will be responders. Using the Chi-square test, a two-sided alpha of 0.05, and 80% power, 27 patients per group will be required. Our final sample size, adjusting for a 10% dropout rate, is 60 (30 per group). Our sample size calculation is based on our intention to treat analysis.

Statistical Analysis: Analysis of our primary outcome will be an intention to treat analysis (using the chi squared test) based on the proportion of patients classified as a responder using the change in the patient perception of bladder condition. A secondary analysis, based on a per protocol analysis (for efficacy) will be performed for patients who completed at least 80% of the treatment sessions for at least 20 min each (determined from patient completed treatment diary, and electronic usage log in the TENS device). Secondary endpoints will be analyzed as appropriate using the students t-test or chi squared test. All data analysis will be carried out using SAS 9.2.

References

2. Ku JH. The management of neurogenic bladder and quality of life in spinal cord injury. *BJU Int*. 2006 Oct;98(4):739–45.
4. Ouslander JG. Management of overactive bladder. *N Engl J Med*. 2004 Feb 19;350(8):786–99.

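### The primary chi-squared test does not adjust for Visit 1 PPBC: it is valid and meets its planned power, but it forgoes some precision and leaves chance baseline imbalance in the estimate

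*Combined protocol and SAP*

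**What the plan says.** - **Test.** The Statistical Analysis section states: "Analysis of our primary outcome will be an intention to treat analysis (using the chi squared test"). No covariate, stratified test or baseline-adjusted sensitivity analysis is planned.
- **Endpoint.** Under Primary outcome measure, of the PPBC: "It is an ordinal scale from 0-5", with higher scores worse. Then: "Patients will be categorized as responders (score improvement by 2 points between screening visit 1 and end of study visit 3) or non-responders".
- **Baseline.** In Figure 1, the row "PPBC Questionnaire" is marked at Visit 1, before randomisation at Visit 2.
- **Design.** Study design describes randomisation by random number generator and mentions no stratification. The Inclusion criteria require symptoms not adequately controlled by earlier measures, but set no minimum PPBC.
- **Sample size.** The Sample size section gives the assumed rates: "we estimate 20% of sham patients and 60% of actively treated patients will be responders". For a chi-squared test at 5% two-sided and 80% power it arrives at 27 per arm, which an allowance of 10% for dropout raises to 30 per arm, 60 in all.

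**The concern.** A fixed 2-point drop on a short bounded scale is not equally attainable from every starting score. A patient at 5 need only reach 3, a patient at 3 must reach 1 or 0, and a patient at 2 must reach 0. Unless the two visits are very highly correlated, high starters also regress further towards the mean. Visit 1 PPBC is therefore a likely prognostic factor for the primary endpoint, and neither the described randomisation nor the analysis uses it as one.

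Two things are at stake. An adjusted test could get more power from the same patients. And with about 30 per group, the arms may differ by chance at Visit 1. Readers would then ask whether baseline explains the result, and an adjustment chosen after unblinding would be open to challenge.

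**Working it through.** **1. The plan's own figure.** Inputs from Sample size: p1 = 0.20, p2 = 0.60, two-sided alpha 0.05, power 80%. With mean proportion 0.40:

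n = [1.960·√(2·0.4·0.6) + 0.842·√(0.2·0.8 + 0.6·0.4)]² / 0.4² = (1.358 + 0.532)² / 0.16 = 22.3.

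The continuity correction gives n' = (n/4)·[1 + √(1 + 4/(n·0.4))]² = 5.583 × (2.203)² = 27.1, which matches the stated 27 apart from rounding. Dropout: 27/0.90 = 30 per group, 60 in all. Exact power at 27 per group is 80.2% with the Yates correction and 86.8% for the uncorrected chi-squared test. At 30 per group the uncorrected test has 90.5%. The planned 80% is met without adjustment.

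**2. What the scale alone implies.** Reading the definition as a drop of at least 2, Visit 1 scores of 0 and 1 cannot respond and scores of 2 to 5 can. Any gradient among 2 to 5 has to be assumed.

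**3. An assumed model.** The documents give no PPBC distribution or correlation. Assumptions: latent normal scores rounded to 0-5, baseline mean 3.8, SD 1.1, shifts solved to give the stated response rates, 30 per group. About 2% of patients then score 0 or 1. At correlation 0.5, sham response is about 9%, 22% and 37% at baseline 3, 4 and 5.

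The comparison is with the Cochran-Mantel-Haenszel (CMH) test. In stratum k, let a be the active responders, m all responders, n1 and n0 the arm sizes, and N = n1 + n0. The statistic is [Σ(a − n1·m/N)]² / Σ[n1·n0·m·(N − m)/(N²(N − 1))], referred to 3.84. Strata are ≤3, 4 and 5.

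| Correlation | 60% v 20%: unadjusted | CMH | 50% v 20%: unadjusted | CMH |
|---|---|---|---|---|
| 0.3 | 0.90-0.91 | 0.94-0.95 | about 0.69 | 0.75-0.76 |
| 0.5 | 0.90-0.91 | 0.93 | about 0.69 | 0.73-0.74 |
| 0.7 | 0.90-0.91 | 0.91 | about 0.69 | 0.71 |

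Ranges reflect repeated runs. At correlation 0.85 the gain is essentially nil. With 27 evaluable per group at 60% v 20%, power is 0.87-0.88 unadjusted and 0.92 / 0.90 / 0.88 with CMH.

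**4. No true effect (20% in both arms).** Overall rejection is 4.7-4.8% for the chi-squared test and about the same for CMH. In roughly 12% of trials the baseline means differ by 0.4 or more. Means of 30 whole-number scores move in steps of 1/30, so the share is about 12% if a gap of exactly 0.4 (12/30) mostly falls outside and 14-15% if every such tie is counted. Within those trials, at correlations 0.3 / 0.5 / 0.7:

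- the responder difference shifts by about 7 / 6 / 4-5 percentage points towards the arm that starts worse;
- the chi-squared test rejects in about 9.4% / 7.4% / 6.5%;
- CMH rejects in about 5-6% / 5% / 4.5-5%.

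In the other 88% the chi-squared test rejects in 4.2-4.5%. At correlation 0.3 these recombine as 0.12 × 9.4% + 0.88 × 4.2% = 4.8%.

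**5. Other assumed baseline patterns.** Six scenarios at 27 per group, with 0% to 30% of patients scoring 0-1 and no to strong dependence above that floor, were analysed with a Mantel-Haenszel test on the single score levels:

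- 60% v 20%: 86-87% unadjusted, 86-96% stratified.
- 50% v 20%: about 66% unadjusted, 64-78% stratified. The low end is a loss of about 2 points (65.8% to 63.7%), where baseline hardly predicts response.
- The largest gain, about 10 points, needs 30% of patients at 0-1. A gain of about 9 points arises with 5% at 0-1 and strong dependence.

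**The case against.** The strongest defence is that nothing here is wrong. A two-proportion test that matches the sample-size calculation is an accepted choice, and the end of the Background section calls the trial a pilot. The test holds its error rate, because chance imbalance is already part of its sampling variation. On the plan's own rates it has power to spare. The 50% v 20% case is illustrative and not the plan's. Suitable strata cannot be known before the baseline distribution is seen. All of this stands, and it limits the size of the point.

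Three stronger readings are tempting, and the documents do not support them:

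- **That type I error is inflated.** The 6.5-9.4% rates apply only to the minority of trials with a marked baseline gap. Over all trials the rate is about 5%.
- **That the trial is underpowered for want of adjustment.** At 60% v 20% the unadjusted test exceeds 80%.
- **That the plan ignores baseline, or that baseline largely decides who can respond.** Response is itself a change from Visit 1. Arithmetic bars only scores 0 and 1, which the entry requirement of inadequately controlled symptoms should make uncommon.

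One part of the defence fails. Defining response as a change from baseline does not adjust for baseline; on a bounded scale it helps to create the dependence.

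**Conclusion.** The point holds as one of precision and interpretation, not validity. A probable prognostic factor, measured on the endpoint's own scale before randomisation, is left out of the primary test, and no stratified randomisation, entry floor or sensitivity analysis makes up for it.

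Under the latent-score model the forgone power is about 0 to 4 points at 60% v 20% and about 0 to 7 points at 50% v 20%. Other assumed patterns run from a loss of 1-2 points to a gain of about 10. For the single trial, a baseline gap of 0.4 or more would move the responder difference by about 4-7 points at correlations of 0.3 to 0.7. The direction follows from the scale. The size rests on a baseline mean, SD and correlation that the documents do not give. The change is worth making because it is cheap; the trial could still be interpreted without it.

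**What to change.** Keep the 2-point endpoint, the intention-to-treat set and the 60 patients. In Statistical Analysis:

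1. Name as primary a CMH test of response by arm, stratified by Visit 1 PPBC.
2. Fix the strata before unblinding (for example ≤3, 4 and 5), collapsing sparse levels from the pooled, blinded baseline distribution.
3. Report the stratum-weighted risk difference with its 95% CI, for example Σw·d/Σw, where d is the stratum difference in response and w = n1·n0/N.
4. Keep the unadjusted chi-squared test as a prespecified sensitivity analysis.

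The cost is a few lines of text and a small change to the SAS code, with no new data, visits or patients. The downside is little or no gain, or a loss of 1-2 points of power, if baseline turns out weakly prognostic or the strata are sparse. Collapsing sparse levels in advance limits the second risk.

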The clinical evidence for the efficacy of percutaneous tibial nerve stimulation for overactive bladder has been well reviewed in a recent systematic review and the AUA/SUFU overactive bladder guidelines(19,20). Variable definitions of success have been used (such as clinical parameters, urodynamic outcomes, and validated patient reported outcome measures), with general success rates of 55-80% after 3 months of treatment, and evidence of efficacy up to 3 years with a monthly maintenance protocol(21). The RCT evidence is summarized in Table 1 below. Across all clinical trials and the systematic review, no serious treatment related adverse effects were seen, and minor adverse events were limited to transient skin irritation, leg cramps or toe/foot pain.

In summary, neurogenic bladder symptoms often have a significant impact on a person's quality of life. A large proportion of people are not well treated with anticholinergic medications, and may not be candidates for intravesical onabotulinum injection. Tibial nerve stimulation is a minimally invasive form of neuromodulation which may be a potential effective treatment, however there is a lack of high quality evidence to support this option. Transcutaneous delivery of electrical current with patch electrodes may be an effective means of tibial nerve stimulation that allows the patient to have the convenience of an at home treatment schedule, with very low associated costs. The objective of this study is to conduct a pilot randomized, sham-controlled, clinical trial to assess the short-term effectiveness of transcutaneous posterior tibial nerve stimulation for patients with neurogenic bladder symptoms that are not adequately controlled with pharmacologic therapy.

Design and methodology

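### Secondary endpoints with a pre-treatment value are left to an unadjusted t-test on an unspecified value; baseline-adjusted ANCOVA would settle the choice and usually add some precision

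*Combined protocol and SAP*

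**What the plan says.** The Statistical Analysis section of the combined protocol and SAP has one sentence on the secondary endpoints: "Secondary endpoints will be analyzed as appropriate using the students t-test or chi squared test". It names no covariate and no regression model, and does not say whether final values or changes are compared. Change from screening is defined only for the primary PPBC responder endpoint.

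Figure 1 shows that pre-treatment values will exist:

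- The row "Qualiveen-SF/NBSS Questionnaire" is marked at Visit 1 (screening) and Visit 3 (end of study).
- The diary row reads "Completed Diary Returned & Provided for Visit 3" at Visit 2, and the pad-test row reads "Pads Returned & Provided for Visit 3" at the same visit. Both are completed again for Visit 3.
- Visit 2 is also the visit of the "Initial 30 minute treatment session in clinic with nurse supervision", so the diary and pads handed in there describe the time before treatment.

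Under Secondary outcome measures, pad weight "will be analyzed for the subgroup of patients with incontinence"; neither the size of that subgroup nor the data that define it are given. The physician assessment is made only at Visit 3 and has no baseline.

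**The concern.** Nine measures have a usable baseline: NBSS, Qualiveen-SF, six diary parameters and pad weight. Two things are at stake for each.

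First, a t-test on the Visit 3 value and a t-test on the change both fit the planned sentence, and they can give different p-values. If the choice is made after the data are seen, the false-positive rate exceeds 5%.

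Second, neither test uses the baseline as a covariate. The trial is sized only for the PPBC responder comparison ("27 patients per group will be required"), and the Background states the aim to "conduct a pilot randomized, sham-controlled, clinical trial". Precision on the secondary endpoints is therefore limited, and data already collected could improve it.

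**Working it through.** **The plan's own figure.** Inputs from the Sample size section: 20% and 60% responders, two-sided alpha 0.05, 80% power.

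- Uncorrected, with mean proportion 0.4: n = [1.96 × √(2 × 0.4 × 0.6) + 0.842 × √(0.2 × 0.8 + 0.6 × 0.4)]² / 0.4² = 22.3 per group.
- With continuity correction: (22.3/4) × [1 + √(1 + 4/(22.3 × 0.4))]² = 27.1.
- The stated 27 is therefore reproduced to within rounding, and 27/0.9 = 30 per group gives the total of 60.

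This concerns the primary endpoint only. It is used below for the arm size after dropout.

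**Assumptions.** The documents give no standardised mean difference (SMD), no SDs and no baseline-to-Visit-3 correlation (r) for any secondary endpoint. I take SMD = 0.6, r from 0.2 to 0.8, and k = baseline SD / Visit 3 SD equal to 1 or 0.7.

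**Open choice.** With k = 1, the final-value and change statistics have correlation (1 − r)/√(2(1 − r)) = √((1 − r)/2), which is 0.5 at r = 0.5. Under no effect, the chance that at least one has p < 0.05 is 8.6%, 8.8%, 9.1%, 9.4% and 9.5% at r = 0.2, 0.3, 0.5, 0.7 and 0.8 (bivariate normal). Simulation at 27 per arm gives 8.7% to 9.7%. ANCOVA alone rejects 4.9% to 5.1%.

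**Precision.** Variance of the arm difference, relative to the final-value t-test:

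- change: 1 + k² − 2rk, which is 2(1 − r) when k = 1;
- ANCOVA: 1 − r², times a small-sample penalty of 1 + 1/(2n − 4).

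Power comes from the non-central t with SMD divided by the square root of the relative variance, n = 27, and 52 degrees of freedom for a t-test or 51 for ANCOVA. With k = 1:

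| r | Final t | Change t | ANCOVA | Gain over better t-test |
|---|---|---|---|---|
| 0.2 | 58% | 40% | 59% | 1 point |
| 0.3 | 58% | 45% | 61% | 3 points |
| 0.5 | 58% | 58% | 70% | 12 points |
| 0.7 | 58% | 80% | 85% | 5 points |
| 0.8 | 58% | 93% | 95% | 2 points |

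At r = 0 ANCOVA has 57%, about 1 point below the final-value test. Over SMD 0.4 to 0.8 and r = 0.2 to 0.8, the gain is 0 to 12 points over the better t-test and about 8 to 37 over the worse.

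**Unequal SDs.** The change score beats the final value when r > k/2, so the crossover is at r = 0.5 only if k = 1. With k = 0.7:

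- r = 0.5: change variance 1 + 0.49 − 0.70 = 0.79, power 68.2%; ANCOVA 69.6%, a gain of 1.4 points.
- r = 0.7: change variance 1 + 0.49 − 0.98 = 0.51, the same as 1 − r². The change t-test has 85.8% and ANCOVA 85.0%, because ANCOVA must estimate a slope that the change score happens to fix correctly.

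**Missing baselines.** With 10% missing at random (assumed) and k = 1, complete-case ANCOVA has 54%, 56%, 65% and 81% power at r = 0.2, 0.3, 0.5 and 0.7. Filling in the overall mean of both arms gives 59%, 60%, 69% and 82%. At r = 0.8 the order reverses (90.6% filled in, 92.6% complete case). At r = 0.85 the filled-in analysis (93.9%) falls below the change t-test (96.0%).

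**The case against.** The strongest case against is that this is a small matter. The endpoints are secondary, about ten measures are listed without multiplicity control, and none is presented as confirmatory. One clause naming the value to compare would remove the false-positive risk without any model. All of that stands, and it keeps the point modest. It does not remove the precision argument: a sponsor who fixes one t-test without knowing r and k may fix the weaker one.

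Four stronger readings are tempting, and the documents do not support them.

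- **The planned t-tests are invalid or biased.** They are not: under randomisation either is valid once it is fixed in advance.
- **The trial has a 9% error rate.** That follows only if both tests are run and the smaller p-value is reported. The plan leaves room for this but does not announce it.
- **ANCOVA always wins, by 12 points.** That figure needs r = 0.5 and equal SDs. Patients enter only after inadequate symptom control, so a narrower spread at baseline is plausible, and then the gain can be about 1 point or slightly negative.
- **Skewed pad weights or episode counts require ranks.** The documents give no distribution. In simulations at 20 per arm and r = 0.5, rank ANCOVA had 52% power against 38% for raw-scale ANCOVA under strong assumed skew (log-SD 1.0), but 52.3% against 51.4% under milder skew (log-SD 0.5). Ranks also give no adjusted difference in grams, which matters in a pilot. Rank analysis is therefore an optional sensitivity analysis.

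**Conclusion.** The point holds as a cheap improvement of modest weight. The plan collects baselines for these endpoints, gives them no covariate role, and leaves final versus change value open. ANCOVA closes that choice, because with baseline in the model the Visit 3 value and the change give the same treatment effect.

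Its benefit over the better t-test ranges from about 12 points of power down to a loss of about 1 point, and over the worse t-test it is usually larger. The two t-tests are equal at r = 0.5 when the SDs are equal. These sizes rest on assumed r, SMD and SD ratio and on 27 analysed per arm; pad weight will have fewer unless every patient is incontinent. A reader might infer that the trial's main conclusion is at risk. It is not: the PPBC responder comparison and the sample size do not depend on this sentence.

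**What to change.** In the Statistical Analysis section, replace the t-test for NBSS, Qualiveen-SF, the diary parameters and pad weight with ANCOVA of the Visit 3 value on arm and the matching baseline value. Report the adjusted difference with its 95% CI. For pad weight, define the incontinent subgroup from pre-treatment data and name the record that defines it. Leave the physician assessment and the primary PPBC responder chi-square as they are.

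State how a missing baseline is handled. Without fill-in, such patients drop out, as they also would from a change score. Overall-mean fill-in is optional: it helps for r up to about 0.7 and costs a little above that.

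The cost is SAP wording and a few lines of SAS code, plus one degree of freedom per model. No new data, visits or patients are needed.
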